13.4.1 Health Economic Analysis Plan

A comprehensive health economic evaluation plan will be developed in line with recent MRC-approved consensus guidance. (14) The aim of the economic evaluation is to address the question "What is the cost-effectiveness, from an NHS perspective over a period of 12 months, of stopping nebulised mucoactive drugs for people with cystic fibrosis established on KaftrioTM, compared to remaining on their standard mucoactive therapy?" It is hypothesised that discontinuation of mucoactive therapy will be a dominant strategy, with reduced cost from reduced mucolytic use, and no change in FEV₁, with reduced treatment time potentially improving QALYs.

Overview of economic analysis

The Base case within-trial economic analysis will use individual participant level data collected over 12 months from the CF-STORM trial. The Base case analysis will undertake a cost utility analysis from an NHS and PSS perspective, in keeping with the NICE reference case. (15) The evaluation will adhere to published guidelines for the economic evaluation of health care interventions as appropriate. (16-18) The within-trial base case economic analysis will compare costs and consequences of each arm over the first 12 months after randomisation. As the trial is only for one year of follow-up, costs and outcomes will not be subject to discounting. It is expected that the majority of costs and benefits associated with the intervention will be captured in this period, and therefore it is not considered necessary to develop a decision-analytic model.

Costs and outcomes

Resource use will be drawn from the UK CF Registry, and valued in monetary terms, with costs per unit estimated using appropriate UK unit costs for the most up to date cost year at the time of analysis. The primary outcome measure for the economic evaluation will be QALYs, estimated using the adult EQ-5D-5L quality of life measure for all participants. Participants aged 12 years and above will self-complete the measure. In participants <12 years, their parent/ legal representative, will be asked to complete the EQ-5D-5L as a proxy for the child. For consistency, where a parent/legal representative completes the baseline EQ-5D-5L, they will be asked to continue doing so, even if during the study their child/adolescent becomes 12 years of age. Utility will be calculated using methods recommended by NICE at the time of analysis, currently NICE recommend the use of the interim scoring system proposed by van Hout and colleagues. (19, 20)

Interpretation

If cost effectiveness analysis reveals that discontinuation of mucoactive therapy results in reduced costs and superior outcomes compared to standard care as hypothesised, discontinuation will be described as 'dominant' and cost effective based on the available evidence. If it is not immediately clear which pathway should be preferred, cost effectiveness will be expressed in the form of an incremental cost effectiveness ratio (ICER), estimated by taking the ratio of the difference in the mean costs and mean outcomes. The economic CF STORM trial HTA 19/160 – NIHR13188916 analysis will use a cost-effectiveness threshold (λ) of £20,000 per QALY, with an ICER below this level indicating that discontinuation of mucoactive therapy is cost effective.

IRAS ID: 293186 Page **50** of **63**

Analysis of uncertainty

Sensitivity analyses will be undertaken to explore uncertainties surrounding key parameters in the economic evaluation in order to investigate how robust the findings are. If the results of the evaluation are not clear, non-parametric bootstrapping will be used to determine the level of sampling uncertainty surrounding the ICER. The bootstrap estimates will be plotted on a cost effectiveness plane, and used to generate cost effectiveness acceptability curves, showing the probability that each treatment arm is cost effective across a range of values of willingness to pay. A secondary analysis of health state utility will be undertaken, reestimating utility using CFQ-R* scores mapped to the EQ-5D-5L measure. (21) This secondary analysis is important as there is some uncertainty regarding the sensitivity and responsiveness of the EQ-5D-5L in cystic fibrosis. (22)

The following additional sensitivity analyses will also be undertaken if appropriate:

- 1. Dealing with missing data (in line with the statistical analysis plan)
- 2. The cost of mucoactive therapy will be varied to test the impact this has on the incremental cost per QALY.
- 3. Costing of resource use in each arm based on the CF Banding tariffs.

Values will be varied to find at what cost, if any, the intervention would switch from being cost ineffective to cost effective or vice versa.

*Participants aged 12 years old and above will complete the adult version of the CFQ-R. Those participants who are aged 6-11 years old will complete the age appropriate version of the CFQ-R.

Secondary analyses

As measures of treatment burden are not included in the EQ-5D-5L, or the domains of CFQ-R that are mapped to EQ-5D-5L using the algorithm developed by Acaster *et al*, we will undertake a secondary cost-consequence evaluation using a partial societal perspective, to present the disaggregated costs and potential benefits of stopping mucoactive therapy. Additional outcomes used in this analysis will include the treatment burden domain scores from the CFQ-R instrument, and the time recorded from nebulisers for the subgroup of patients for whom this data will be available.

IRAS ID: 293186 Page **51** of **63**

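### The rule that an ICER below £20,000 per QALY favours stopping gives the opposite answer when stopping saves money but loses QALYs

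*Protocol*

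**What the plan says.** All of this is in Protocol section 13.4.1, Health Economic Analysis Plan.

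- **Expected result.** The hypothesis is that "discontinuation of mucoactive therapy will be a dominant strategy, with reduced cost from reduced mucolytic use". QALYs are expected only potentially to improve, through less treatment time. Section 5.3.2 says much the same.
- **Interpretation, first step.** If stopping is both cheaper and better, it is called dominant and the matter ends there.
- **Interpretation, second step.** "If it is not immediately clear which pathway should be preferred, cost effectiveness will be expressed in the form of an incremental cost effectiveness ratio", which is "estimated by taking the ratio of the difference in the mean costs and mean outcomes".
- **Threshold and rule.** The analysis uses a "cost-effectiveness threshold (λ) of £20,000 per QALY", "with an ICER below this level indicating that discontinuation of mucoactive therapy is cost effective". Nothing is said about a negative QALY difference, and net benefit is not mentioned.
- **Analysis of uncertainty.** Sensitivity analyses on key parameters are planned without condition. Two of them vary the cost of mucoactive therapy and look for the cost at which the conclusion switches. The bootstrap, the cost-effectiveness plane and the acceptability curves are conditional: "If the results of the evaluation are not clear, non-parametric bootstrapping will be used to determine the level of sampling uncertainty".

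**The concern.** The familiar rule that an ICER below the threshold means cost effective was made for a new treatment that costs more and does more. Here the strategy under test removes drugs and is expected to cost less. If stopping is cheaper and better, no ICER is needed. If it is cheaper and somewhat worse on QALYs, the ICER step is reached, and the ratio then means pounds saved per QALY given up. A decision-maker wants that figure to be high. The protocol's rule treats a low figure as support for stopping.

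Value for money of the STOP strategy is a listed outcome in section 9.2, and sections 5.2 and 17.2 say the results are meant to inform NICE. Read literally, the rule could turn a correct set of costs and QALYs into the opposite recommendation.

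**Working it through.** The protocol states no cost or QALY difference, so there is no figure of its own to reproduce. The check compares the literal rule with net benefit at the protocol's threshold.

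**Inputs.** λ = £20,000 per QALY (section 13.4.1). ΔC and ΔQ are the differences in mean cost and mean QALYs, STOP − CONTINUE. All values of ΔC and ΔQ below are assumptions chosen to show direction.

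**Formulas.**
- ICER = ΔC / ΔQ.
- Incremental net monetary benefit, INMB = λ × ΔQ − ΔC. STOP is cost effective if INMB > 0.
- INMB > 0 means ΔC < λ × ΔQ. If ΔQ > 0, dividing by ΔQ gives ICER < λ, which is the protocol's rule. If ΔQ < 0, dividing by ΔQ turns the inequality round and gives ICER > λ.

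The direction of subtraction cannot rescue the rule. Taking CONTINUE − STOP changes the sign of both differences and leaves the ratio the same. Seen that way, CONTINUE is the dearer and better option, and a ratio below £20,000 means that continuing is cost effective.

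**Examples.**

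| Case | ΔC (£) | ΔQ | ICER (£) | Literal rule on STOP | INMB (£) | Net benefit on STOP |
|---|---|---|---|---|---|---|
| Cheaper, worse | −500 | −0.10 | 5,000 | accept | −2,000 + 500 = −1,500 | reject |
| Cheaper, worse | −5,000 | −0.10 | 50,000 | reject | −2,000 + 5,000 = +3,000 | accept |
| Cheaper, worse | −3,000 | −0.05 | 60,000 | reject | −1,000 + 3,000 = +2,000 | accept |
| Cheaper, worse | −3,000 | −0.30 | 10,000 | accept | −6,000 + 3,000 = −3,000 | reject |
| Dearer, better | +500 | +0.05 | 10,000 | accept | 1,000 − 500 = +500 | accept |
| Dearer, better | +3,000 | +0.05 | 60,000 | reject | 1,000 − 3,000 = −2,000 | reject |

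**Range.** Over a grid of assumed savings from £200 to £6,000 and QALY losses from 0.001 to 0.399, leaving out exact break-even, the literal rule disagreed with net benefit at all 23,482 points. The algebra says it must: this is a full reversal within that quadrant, not an edge case.

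**Break-even.** The QALY loss that a saving just justifies is saving / 20,000: 0.05 at £1,000, 0.15 at £3,000 and 0.25 at £5,000. Below that loss stopping is worthwhile and the rule says it is not; above it, the other way round.

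**Effect on the planned cost-threshold analysis.** Hold the loss at an assumed 0.10 QALY and vary the drug saving. At £3,000 the ICER is £30,000 (rule: reject) and INMB is −2,000 + 3,000 = +£1,000. At £1,000 the ICER is £10,000 (rule: accept) and INMB is −2,000 + 1,000 = −£1,000. The switch is found at the right place, a saving of £2,000, but with its direction reversed: stopping appears to become better value as the drugs it saves become cheaper.

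**The case against.** The strongest reply is that an unnoticed reversal is unlikely. A cheaper-but-worse result is plausibly one that the plan would call unclear, which would trigger the bootstrap, the cost-effectiveness plane and the acceptability curves. The plane would show the points in the saving-and-loss quadrant, and curves computed by net benefit would be right. A separate health economics plan is also announced, and the evaluation is to follow published guidelines. This bears on the likelihood of harm and lowers the severity. It does not correct the rule: correct curves would contradict the stated interpretation, and the choice between them would be made after the results are known. Nor is this a detail left to a later plan, since the protocol itself fixes the rule.

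Three stronger readings are tempting, and the documents do not support them.

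- *The rule also accepts a dominated result.* If STOP is dearer and worse, the ratio is negative and so numerically below £20,000. But the ICER is used only where the preferred pathway is not immediately clear, and in that case it is clear. The protocol names only dominance by STOP, so naming the opposite case would be a useful clarification and no more.
- *There is about a 50% chance of landing in the reversed quadrant.* That needs a true QALY difference of exactly zero and a near-certain saving. The protocol hopes for a QALY gain, which would lower the chance, and gives no figures from which to calculate it.
- *A dominant result could be reported with no uncertainty at all.* The sensitivity analyses and the secondary utility analysis mapped from the CFQ-R are unconditional. Only the bootstrap and the displays built on it depend on the results being unclear.

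**Conclusion.** The rule is wrong as written for one quadrant. When STOP saves money and loses QALYs, it returns the opposite of the net-benefit decision at £20,000 at every point except break-even. When STOP costs more and gains QALYs, it is correct. Because the protocol expects lower cost, the reversed quadrant is the main trade-off that the ICER step would have to handle.

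The reversal itself rests on algebra and on the protocol's own definition and threshold. The pound and QALY values are assumed and are not estimates for this trial. The point should be fixed before analysis, but its reach is limited: the same costs, QALYs and ICER would be computed, and only their reading changes. The primary ppFEV1 analysis and the sample size are untouched.

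**What to change.** Replace the decision sentence in section 13.4.1 with a net-benefit rule: STOP is cost effective if £20,000 × (QALY difference, STOP − CONTINUE) − (cost difference, STOP − CONTINUE) is above zero. Because it does not divide by the QALY difference, this rule also works when that difference is close to zero. Alternatively, keep the ICER and state that when the QALY difference is negative it must exceed £20,000 for stopping to be cost effective. Use the same criterion in the analyses that vary mucoactive drug cost and look for the switching point, and carry it into the health economics plan.

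A separate, optional suggestion: run the bootstrap, plane and acceptability curve whatever the point estimate shows, so that a dominant result also comes with its sampling uncertainty.

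The cost is a sentence or two in the protocol and the health economics plan, and trivial analysis work.

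### The hypothesised dominant result could be reported with no sampling uncertainty, because the bootstrap is run only when results are 'not clear'

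*Protocol*

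**What the plan says.** All of the relevant text is in Protocol Section 13.4.1.

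- **Hypothesis.** "It is hypothesised that discontinuation of mucoactive therapy will be a dominant strategy". Lower drug cost is expected, with only a potential gain in QALYs.
- **Outcome.** "The primary outcome measure for the economic evaluation will be QALYs", derived from the EQ-5D-5L.
- **Dominance rule (Interpretation).** The condition is that "discontinuation of mucoactive therapy results in reduced costs and superior outcomes compared to standard care as hypothesised". The consequence is that "discontinuation will be described as 'dominant' and cost effective based on the available evidence". No interval, probability or test is named.
- **When an ICER is calculated (Interpretation).** "If it is not immediately clear which pathway should be preferred, cost effectiveness will be expressed in the form of an incremental cost effectiveness ratio". It is judged against £20,000 per QALY.
- **Sampling uncertainty (Analysis of uncertainty).** "If the results of the evaluation are not clear, non-parametric bootstrapping will be used to determine the level of sampling uncertainty surrounding the ICER". The next step depends on it: "The bootstrap estimates will be plotted on a cost effectiveness plane, and used to generate cost effectiveness acceptability curves".
- **Unconditional work.** "Sensitivity analyses will be undertaken to explore uncertainties surrounding key parameters in the economic evaluation". Utility is also to be re-estimated from the CFQ-R. Further analyses of missing data, mucoactive therapy cost and banding tariffs are to be done where appropriate.

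The section also says that a full health economic plan will be developed.

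**The concern.** Whether an economic result is clear depends on how precisely the cost and QALY differences are estimated. The protocol measures that precision only after the result has been judged unclear, so the rule is circular. Because 'clear' has no definition, the judgement is made after the results have been seen.

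The rule is also uneven. If the point estimates show lower cost and higher QALYs, the preferred option looks clear, no ICER is called for and nothing triggers the bootstrap. The result that the investigators hypothesise is the one most likely to escape the check.

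The QALY difference may well be small. Section 13.1.1 assumes a ppFEV1 difference of 0, and Section 13.4.1 notes that the EQ-5D-5L does not measure treatment burden and may be insensitive in cystic fibrosis. Close to zero, the sign of an estimate is largely chance. At stake is how firmly an economic finding is stated when, by Sections 5.2 and 17.2, it is meant to inform the NICE appraisal.

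**Working it through.** **1. Does anything else in the protocol cover sampling error in the economic result?**

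- Sensitivity analyses on key parameters vary inputs. They do not measure sampling error.
- The CFQ-R mapping changes the utility source and does not measure sampling error either.
- The three listed extras are themselves conditional and address other matters.
- Section 13.4 sets a 2.5% level and one-sided 97.5% intervals, and names quality of life scores among the continuous outcomes. It does not name QALYs, costs or the ICER.

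The bootstrap is therefore the only stated assessment, and it is conditional.

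**2. Sample size for the illustration.** The economic section states no sample size, so the evaluable number for the primary outcome is used. Inputs from Sections 13.1.1 and 13.1.2 are a margin of 3, SD 12.1, expected difference 0, one-sided 0.025 and 80% power.

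n per arm = 2 × 12.1² × (1.960 + 0.842)² / 3² ≈ 255.4, so 256. The protocol states 257, which is reproduced to within one participant. Allowing for dropout, 257 / 0.90 = 285.6, so 286 as stated. The illustration uses 257 per arm.

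**3. Chance that the point estimates show dominance.** Two assumptions are needed, because the protocol gives no figures: an observed cost saving is certain, and the QALY SD lies between 0.05 and 0.20.

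SE = SD × √(2/257) = SD × 0.0882

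P(estimated QALY difference > 0) = Φ(true difference / SE)

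| Assumed QALY SD | SE | 95% half-width (1.96 × SE) | True difference 0 | True loss 0.005 | True loss 0.01 |
|---|---|---|---|---|---|
| 0.05 | 0.0044 | 0.0086 | 50% | 12.8% | 1.2% |
| 0.10 | 0.0088 | 0.0173 | 50% | 28.5% | 12.8% |
| 0.15 | 0.0132 | 0.0259 | 50% | 35.3% | 22.5% |
| 0.20 | 0.0176 | 0.0346 | 50% | 38.8% | 28.5% |

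The 50% does not depend on the SD. If an observed saving is only 90% or 80% likely, and independent of the QALY estimate, it becomes 0.90 × 0.50 = 45% or 0.80 × 0.50 = 40%.

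**4. What a mislabel means for the decision.** A loss of 0.01 QALY is worth 0.01 × £20,000 = £200. Stopping would still be cost effective at the protocol's threshold if it truly saved more than £200 per participant.

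**The case against.** The strongest defence is that the two conditions match. The bootstrap is described as concerning the ICER, and an ICER is calculated only when the preferred option is not obvious. An ICER is also a poor summary when one option appears dominant. On this reading the protocol leaves the dominant case uncovered but does not rule out intervals for it. It also names a fuller health economic plan, the NICE reference case and published guidelines, any of which may lead to bootstrapping in every case.

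Part of this stands. Nothing prohibits reporting intervals, and the fuller plan is not at hand. But the protocol is not merely silent: it sets a condition on the bootstrap. A general promise to follow guidelines as appropriate does not remove it, and the circularity remains even if 'not clear' was meant to include statistical uncertainty.

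A reader might infer two stronger points, and the documents support neither.

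- *Costs are almost certain to fall.* Section 13.4.1 only hypothesises this and gives no cost figure. Admissions, intravenous days and extra antibiotics, all outcomes in Section 9.2, could offset drug savings.
- *Stopping would wrongly be judged cost effective.* With a true QALY difference of 0 and a real saving, stopping is cost effective and only the word 'dominant' is wrong. With a 0.01 QALY loss, the decision is still right at £20,000 if the saving exceeds £200.

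**Conclusion.** The point holds as a weakness in how the economic result would be judged and reported. The protocol attaches no interval or probability to a declaration of dominance, and makes its only assessment of sampling uncertainty depend on an undefined judgement that cannot be made without it.

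The percentages show how easily a small QALY difference can take a favourable sign. They rest on the assumed SDs, the assumed true losses, 257 evaluable per arm and a certain observed saving, so they are illustrations and not estimates for this trial. They measure the risk to the label and its implied certainty, and do not demonstrate a wrong adoption decision. The finding concerns a secondary objective. The ppFEV1 non-inferiority conclusion, the sample size and data collection are untouched.

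**What to change.** In Section 13.4.1, delete the opening condition on the bootstrap and carry the change into the health economic plan before any economic analysis:

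- Bootstrap costs and QALYs jointly in every case, whatever the point estimates.
- Always report intervals for incremental costs and incremental QALYs, the cost-effectiveness plane, the acceptability curve, and the probability that stopping is cost effective at £20,000 per QALY.
- Use 'dominant' only alongside these results.

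Participant-level data are already planned, so no new data are needed. The cost is one wording change and a few hours of analysis.

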14 DATA MANAGEMENT AND TRIAL MONITORING

For the CF STORM trial the responsibilities for Data Management and monitoring are delegated to the LCTC. Separate Data Management and Trial Monitoring Plans have been developed which provide detail regarding the internal processes that will be conducted at the LCTC throughout the trial. Justification for the level of monitoring is provided within those documents and the trial-specific risk assessment. All data will be managed as per local LCTC processes and in line with all relevant regulatory, ethical and legal obligations.

14.1 Source Documents

The UK CF Registry and CF STORM Module will be considered the source document for data where no prior record exists and which is recorded directly in the UK CF Registry and CF STORM Module. A CF STORM source document list will be produced for each site to be kept in the ISF and provide detail of what constitutes CF STORM-specific source data.

Date(s) of informed consent (and assent where appropriate) processes, including date of provision of patient information, Study Identifier and the fact that the patient is participating in a clinical trial (including possible treatment arms) must be added to the patient's medical record chronologically.

14.2 Data Collection Methods

The UK CF Registry is the primary data collection instrument for the trial. Data entered routinely in the UK CF Registry will be used alongside CF STORM Module's specific data fields in order to collect the data required. The UK CF Registry is a web-based remote data entry system that captures information for each CF visit (encounter). Data should be entered on an encounter basis, clinics should aim to enter data on the UK CF Registry and manually transfer the data over to the CF STORM Module within three weeks of an encounter and certainly no later than six weeks after the encounter. Where centre staff are aware of a SAR/Related SAE, data should be entered more promptly in line with the SAR reporting timelines specified in section 12.2 of the protocol. Training will be provided to sites for the CF STORM Module prior to any data entry.

14.3 **Monitoring**

Monitoring is conducted to ensure protection of patients participating in the trial and all aspects of the trial (procedures, trial intervention administration and data collection) are of high quality and conducted in accordance with sponsor and regulatory requirements.

A detailed Trial Monitoring Plan will be developed and agreed by the TMG and CI to describe who will conduct the monitoring, at what frequency monitoring will be done, and what level of detail monitoring will be conducted. This will be dependent on the documented risk assessment of the trial which determines the level and type of monitoring required for specific hazards. All processes may be subject to monitoring, e.g. enrolment, consent, adherence to trial interventions, accuracy and timeliness of data collection etc.

Trial Oversight Committees related to the monitoring of the trial are detailed in Roles and Responsibilities see section 4.

